Many significant psychosocial changes for stroke survivors and their partners may not occur until at least 6-12 months post-stroke when the couple is attempting to re-integrate into “normal” life. For example, there may be significant role changes (e.g., new caregiver role) and role losses or reversals (e.g., primary provider is no longer able to work). This can be a source of stress for both partners in the relationship. McKevitt et al. (2011) (13) found that nearly half (42%) of respondents with a partner at the time of stroke reported a negative change in the relationship. Social support and relationship harmony also deteriorate significantly from 1-3 years post-stroke while depressive symptoms increase (14). Couples with increased negativity in their relationships have worse psychological outcomes, including depression (15). A recent systematic review examining perceived changes in social support after stroke observed significant strain within the family unit after stroke and that this was associated with depression and severity of disability (16).

A new model is needed for stroke survivors and partner caregivers that focuses on the remaining relationship strengths in order to foster resilience in the couple. Despite the high prevalence and significant consequences of post-stroke depression, diagnosis and treatment of depressive symptoms in stroke survivors and caregivers are often inadequate. Support for efficacy of existing psychotherapeutic interventions for post-stroke depressive symptoms, such as cognitive-behavioral therapy, is mixed (17). Positive psychology interventions (PPIs) may be particularly useful as they aim to increase well-being by promoting positive emotions, thoughts and behaviors. Based on the broaden-and-build theory (18), PPI-induced positive emotions can broaden thought-action repertoires, which, in turn, create behavioral flexibility that over time builds personal resources such as resilience, social closeness, and even physical health (19). Research suggests that post-stroke positive emotionality is associated with improved function and social participation (20, 21). PPIs could be an effective treatment for stroke survivor *and* caregiver depressive symptoms.

Because of the reciprocal psychosocial effects of stroke (22), recent trends in the stroke

survivor/caregiver literature have espoused the **benefits of using a dyadic approach** (1, 23), with a recent review of caregiver and dyad interventions (1) supporting dyadic intervention use for targeting stroke survivor outcomes such as mood (depression and anxiety), social function, physical function and health-related quality of life (Class IIa; Level of Evidence A). Yet, dyadic interventions are scarce, rarely involving more than information and education (23-25). Interventions that include skill-building (e.g. problem solving, stress management, and goal setting) are recommended over those consisting of psychoeducation or support only. PPIs include these skill building components; for example, strategies to focus on the positive, deep breathing techniques for mindfully savoring a moment, and learning how to work toward a goal. However, findings for dyadic interventions are less clear for the caregiver's well-being (1). This is likely because existing dyadic interventions are focused on stroke survivor needs (1). **Our PPI is designed to respond to both caregiver and survivor needs** by having them complete PPI activities individually and together as a couple.

This intervention is innovative in being **the first dyadic PPI aimed at couples coping with stroke to enhance mood and well-being**. Most traditional psychological approaches for stroke survivors focus on deficits and treatment of negative mood states, and have limited support for efficacy in treating post-stroke depressive symptoms (17). PPIs, in contrast, are based on enhancing psychological strengths and resources to increase well-being (26). Though not currently tested in stroke, PPIs have been effectively applied to various medical populations, including individuals with diabetes, spinal cord injury, or breast cancer (27-30), and have been shown to significantly increase well-being and decrease depressive symptoms (26, 31, 32) with long-lasting effects (28). PPIs carry little to no side effects, are less expensive and time consuming than psychotherapy, and involve minimal additional burden as they consist of brief, self-administered activities.

PPIs are typically targeted at the individual. However, due to the reciprocal nature of positive affect and positive close relationships (33), PPIs are ideally suited as a dyadic intervention. **In our innovative dyadic approach**, stroke survivors and caregivers complete PPIs each week on their own and together. Further, we are also examining **potential mechanisms of the dyadic PPI on couples' mood** through interactions and shared emotional processes. Research on emotion co-regulation supports the notion that mood states among family members are correlated (34). By having participants complete PPI activities on their own we expect that individual positive emotion will increase. Through PPI activities completed together, couples will share in positive experiences, thereby increasing positive affectivity and strengthening social bonds. Together, this can foster a more positive environment over time, and effect a synergistic change in positive affect and well-being for the dyad. Couples with greater well-being may be better emotionally equipped to handle the stresses of stroke, potentially reducing depressive symptoms (10, 12). Although our intervention is developed for and will be tested in local, community-dwelling couples post-stroke, it is developed so that it is easy to administer using telehealth where the intervention could benefit those geographically or situationally isolated.

Preliminary Data

With internal funding (University of Utah's Consortium for Family and Health Research (C-FAHR)), we have collected preliminary feasibility data on the proposed dyadic PPI (IRB_00080565). We developed the positive psychology activities booklet to be used in our PPI

protocol and sent it to 5 clinical, stroke survivor and caregiver stakeholders for readability, acceptability and applicability. We modified materials based on their feedback.

Aim 1. To determine preliminary efficacy of the PPI in 24 couples with depressive symptoms in a randomized waitlist control pilot trial on mood and well-being. *H1a: The PPI will improve well-being and mood as assessed by established outcome measures in survivors and caregivers from pre- to post-intervention. H1b: Improvements in well-being and mood will be greater in the PPI vs. control group.*

Aim 2. To determine if the PPI improves quality of interactions in couples during stressful discussion and collaborative problem-solving tasks. *H2: The PPI will enhance the emotional tone of the couple’s interactions from pre- to post-intervention as measured by observational interaction coding.*

Exploratory Aim 3. To determine whether increases in mood in one partner leads to improvement in mood in the other partner over time as assessed by weekly self-report. *H3: Increases in mood in one partner will be positively associated with increase mood in*

the other partner and vice-versa; i.e. be synergistic across couples.

Study Population

Age of Participants: 18+, no upper limit

Sample Size:

At Utah: 70

All Centers:

Inclusion Criteria:

Inclusion criteria are:

- 1) Couples consisting of one partner who had an ischemic or hemorrhagic stroke ≥ 6 months ago and a cohabiting partner (living together ≥ 1 year) who self-identifies as the caregiver and is willing to enroll in the study.
- 2) Either one or both partner(s) report depressive symptoms as assessed by the PROMIS-Depression measure (no formal diagnosis is required).
- 3) Both partners must be community-dwelling adults age 18 years and older.
- 4) Both partners must be able to understand printed English instructions

Exclusion Criteria:

Exclusion criteria are:

- 1) Either partner does not consent to participate.
- 2) The caregiving partner has had a stroke or other major neurological condition.
- 3) Either partner is unable to understand printed English instructions.
- 4) Either partner has significant cognitive impairment (as assessed by the Telephone Interview for Cognitive Status, TICS).

Note: As this is a pilot study, we are restricting participation to only those who are able to understand printed English instructions and have mild/no cognitive impairment. We anticipate expanding inclusion criteria for future trials.

Design

Survey/Questionnaire Research

Prospective Clinical Research
Randomized
Phase I Clinical Trial
Other

Randomized wait-list controlled pilot trial of a behavioral intervention

Study Procedures

Recruitment/Participant Identification Process:

Based on preliminary feasibility data (see Preliminary Studies), we are estimating 80% retention but will conservatively plan for only 70%. To ensure a total of 24 dyads (12 PPI, 12 control) for pilot data analysis, we plan to enroll 35 couples.

Participants will be recruited through University-affiliated clinics, stroke- and caregiver-related support groups, research participant databases, and the University of Utah's Clinical Trials webpage. We have established relationships with these clinics to assist with recruitment, including the Outpatient Rehabilitation Psychology Clinic, Neurology Stroke Clinic, Rehabilitation and Wellness Clinic, and Stroke Rehabilitation Clinic. Research assistants (RAs) will recruit in clinics. We will also provide study information to staff and health care providers along with recruitment letters to hand out to interested potential participants (referral).

We will also distribute study flyers to local support groups (e.g. aphasia, stroke survivor, caregiver support groups). Finally, we will also send recruitment letters to people listed in research participant databases. Recruitment materials will state that they can contact us for more information about study participation. Responding to the letter/flyer is not consent to participate, just for information. Interested people will be pre-screened on the phone for minimum inclusion criteria (couple with one partner having had stroke 6 or more months ago, both are willing to participate, one or both partners are reporting some depressive symptoms).

Informed Consent:

Description of location(s) where consent will be obtained:

Consent will be obtained during participants' first in-person visit prior to completing baseline survey material in the Occupational Therapy Life Skills Clinic.

Description of the consent process(es), including the timing of consent:

Once participants have been screened on the phone or at the clinic, they will receive a copy of the informed consent for their review. Consent will be obtained at the beginning of their first in-person visit prior to completing baseline survey material. The investigator or research assistant will review the informed consent document with the participant. Participants will have an opportunity to review materials on their own and ask questions prior to consenting to participate (or opt out of participating). Both members of participant couples will sign a single consent document.

Procedures:

Potential participants will be screened verbally over the phone (if responding to recruitment letter or flyer or referral from clinic) or in person (if seen at clinic). If screened in person, this will be done in a clinic room where privacy and confidentiality can be maintained. Potential participants will be asked about time since stroke, whether they are experiencing mood changes or have difficulty enjoying things they used to enjoy (or if their partner is experiencing these symptoms), and if they have a partner/spouse who is willing to participate as well. Cognitive functioning will be evaluated using the Telephone Interview for Cognitive Status (TICS), which is a brief, standardized test of cognitive function that can be administered over the phone or in person. If minimum criteria are met, participants will be enrolled.

Following screening, eligible dyads will be adaptively randomized into PPI and waitlist control groups based on sex of the stroke survivor. PPI dyads will partake in 3 in-person study sessions at the Occupational Therapy's Life Skills Clinic: pre- (T1:baseline), post- (T2), and 3-months post-intervention (T3). Waitlisted dyads will complete a waitlist baseline assessment (T0), followed by T1, T2, and T3 assessments.

T1 session: Dyads will complete baseline surveys (see Appendix). In order to reduce burden and fatigue, we split the survey packet into two packets: one that is mailed ahead that participants complete at home and bring to their session, and a second packet that is completed at the clinic. The latter survey packet contains the more sensitive questionnaires (e.g. mood measures, asking about relationship quality) and participants complete these in separate rooms to allow for privacy in answering potentially sensitive questions. We will also collect observational data on the couple's interaction dynamics. Participants will engage in two dyadic interaction tasks (together in the same room), which will be digitally recorded: (1) a structured discussion task and (2) a collaborative problem-solving task. Both of the dyadic tasks we are using are widely used among couples' researchers (37-40). The first task consists of two prompted 5 minute discussions on a) a neutral (baseline) topic such as a television program they watch and b) a negative topic. We are interested in learning how a couple handles discussing a stressful topic. Topics for the stressful discussions will be chosen from a list of common areas of disagreement for couples (e.g., household responsibilities, communication, health and exercise) based on dyad match (i.e. both participants in a couple nominate the topic) and valence (topic is rated as appropriately stressful). The second dyadic task consists of a collaborative cognitive task in which the couple is asked to imagine that they need to run a list of errands for a trip (e.g., pick up medication, withdraw money at the bank) (38). They are provided a map of a fictitious community with locations for stops for their errands list. The couple then generates a plan that specifies the 5 most important errands they plan to complete, the order in which they complete them, and the route they plan to take. We selected this task because we are interested to learn how the couple collaborates during problem-solving on a task that mirrors the types of everyday decisions couples make. Following each dyadic task, we will administer a brief affect measure as a manipulation check (the stressful discussion task, for example, should have evoked more negative emotion than the neutral task), and a measure to assess perception of the task and their partner during the task.

Intervention: The PI or a trained RA will train participants in the activity exercises. We selected PPI activities on empirically supported evidence for efficacy in improving depressive

symptoms and/or increasing well-being (26, 31, 32). We have adapted them to be completed individually and together as a couple. Based on existing research suggesting that practicing a variety of self-selected PPI activities produces more sustained increases in well-being (44), participants are instructed to select PPI's from a menu (Table 1) and to complete at least two PPI activities alone and two together each week for 8 weeks. They are encouraged to perform the activities especially on "bad" days (feeling down). They will each be given a booklet containing descriptions of these activities (with examples) and a tracking calendar to help complete activities at home.

Table 1. Positive psychology activities

Expressing gratitude	Counting blessings, appreciation of life circumstances and gratitude to (thanking someone) by writing or expressing gratitude directly to another person.
Practicing acts of kindness	Performing good deeds for other people, whether friends or strangers, or anonymously, either spontaneously or planned.
Fostering relationships	Strengthening and enjoying relationships by making time for people, expressing appreciation, and affection, and being supportive.
Focusing on the positive	Replaying positive experiences and self-monitoring instances of well-being (e.g., listing three good things that happened that day).
Savoring	Taking delight, and replaying life's momentary pleasures and wonder to finding beauty, relishing ordinary experiences, and savoring those experiences with others.
Working towards a goal	Picking one or two significant goals that are meaningful and devoting time to pursuing them.
Spirituality	Becoming more involved in religion or spirituality by, for example, seeking meaning and purpose, finding the sacred in ordinary life, and meditating.

The RA will call participants weekly to collect data on mood and remind participants to complete and mail in their weekly check-in surveys. These check-in surveys include the tracking calendar page for that week and a series of questions about mood and other changes in behavior for that week (see appendix). Participants also have an opportunity to ask questions at these check-in calls.

Post-intervention and 3-month follow-up sessions: At post-intervention (T2) and 3-month follow-up (T3), participant dyads will return to the Life Skills Clinic to complete study measures. At T2, the dyads will complete surveys and engage again in the two dyadic interaction tasks. The dyads will also complete a post-program feedback questionnaire and semi-structured interview. Feedback will be incorporated into future intervention protocols. At T3, dyads will complete a final set of surveys and a final brief interview to assess whether they continue to engage in the PPI activities and to discuss barriers and/or supports for continuing these activities. Dyads will be compensated for their time at each testing session and weekly check-in surveys they complete.

Procedures performed for research purposes only:

Statistical Methods, Data Analysis and Interpretation

Study data will be maintained in REDCap (Research Electronic Data Capture tools), a highly secure, web-based application designed to support data capture. The **University of Utah Study Design and Biostatistics Center will guide statistical analyses.** We will calculate response, recruitment, and attrition rates. PPI acceptability will be assessed post-treatment using a satisfaction survey and a feedback interview. Participants will indicate overall benefit, negative effects, and intervention satisfaction.

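### Negative effects of the PPI are asked about explicitly only after treatment, with no enquiry described for couples who leave, so the reported result may understate them

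*Combined protocol and SAP*

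**What the plan says.** Under Statistical Methods, Data Analysis and Interpretation, the protocol states: "PPI acceptability will be assessed post-treatment using a satisfaction survey and a feedback interview. Participants will indicate overall benefit, negative effects, and intervention satisfaction". This fits the description of T2 under Post-intervention and 3-month follow-up sessions: "The dyads will also complete a post-program feedback questionnaire and semi-structured interview". The T3 visit has a different purpose: "a final brief interview to assess whether they continue to engage in the PPI activities and to discuss barriers and/or supports for continuing these activities". Negative effects are not named there.

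During the 8 weeks of activities there is regular contact. Under Intervention: "The RA will call participants weekly to collect data on mood and remind participants to complete and mail in their weekly check-in surveys". The weekly survey covers activity tracking, mood and changes in behaviour. Its items are in an appendix.

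On losses, the Recruitment/Participant Identification Process section says: "we are estimating 80% retention but will conservatively plan for only 70%. To ensure a total of 24 dyads", and sets enrolment at 35 couples. The statistical section undertakes to report attrition as a rate. It does not mention reasons for leaving. The available text describes no early-termination assessment and no adverse-event collection.

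**The concern.** Leaving is a natural response to an intervention that a couple finds upsetting. A question put only after the course tends to miss the couples most likely to answer yes to it. Overall benefit and satisfaction are collected with the same survey and interview, so they are open to the same selection.

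This matters because the background section presents the intervention as the first dyadic PPI for couples coping with stroke, and starts from the premise that PPIs have few if any side effects. The pilot is the first chance to check that premise in this population, and the feedback is meant to shape later versions of the intervention. A favourable result drawn mainly from couples who stayed would be weak evidence for the premise.

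**Working it through.** **Step 1. Reproduce the enrolment figure.** Inputs from the recruitment section: 24 couples needed, 70% planned retention, 80% expected retention.

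24 / 0.70 = 34.3, rounded up to 35. This matches the stated 35.

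**Step 2. Couples who could lack a post-treatment record.**

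- At 70% retention: 35 × 0.70 = 24.5. Taking the 24 couples the plan needs, 35 − 24 = 11, and 11/35 = 31.4%.
- At 80% retention: 35 × 0.80 = 28, so 35 − 28 = 7, and 7/35 = 20.0%.

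Both counts are upper limits for couples exposed to the PPI, for two reasons. Some couples may leave before starting it, for example while waitlisted. Others may leave between T2 and T3, when they have already answered. The protocol does not say at which visit retention is counted.

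**Step 3. How far the result could be off.** The documents give no rate of negative effects and no reasons for loss, so the rates here are assumptions. Let 5% of couples who attend T2 report a negative effect, and let a proportion h of lost couples have had one. The rate over all 35 is (attending × 0.05 + lost × h) / 35.

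| h among lost couples | 70% retention (24 attend, 11 lost) | 80% retention (28 attend, 7 lost) |
|---|---|---|
| 5% (loss unrelated) | 5.0% | 5.0% |
| 20% | (1.2 + 2.2)/35 = 9.7% | (1.4 + 1.4)/35 = 8.0% |
| 30% | (1.2 + 3.3)/35 = 12.9% | (1.4 + 2.1)/35 = 10.0% |
| 40% | (1.2 + 4.4)/35 = 16.0% | (1.4 + 2.8)/35 = 12.0% |

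The reported figure would be 5% in every cell. The first row shows that there is no bias if leaving is unrelated to negative effects.

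**Step 4. A reassuring-looking result.** Suppose no couple at T2 reports a negative effect. The exact 95% interval is 0 to 14.2% for 0/24 and 0 to 12.3% for 0/28. These intervals describe sampling error among attenders only. If k lost couples had left because of a negative effect, the share of all enrolled would be k/35: 2.9% for k = 1, 8.6% for k = 3 and 14.3% for k = 5. The ceiling, at which every lost couple had one, is 31.4% at 70% retention and 20.0% at 80%.

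**Step 5. Compare what is collected, and from whom.**

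| Source | Asks explicitly about negative effects? | Covers couples who leave early? |
|---|---|---|
| Weekly call and survey | Not described; items in an unavailable appendix | Yes, until they leave |
| T2 survey and interview | Yes | Only if they attend T2 |
| T3 interview | Not named | Only if they attend T3 |
| Attrition rate | No; reasons not mentioned | Yes, as a count |

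No source is described as both asking the question and reaching couples who leave.

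**The case against.** The strongest reply is that couples who leave do contribute data. Mood is collected weekly from both partners, along with changes in behaviour, and Aim 3 uses every week that a couple supplies, including from drop-outs. A couple whose mood falls before leaving leaves a trace of that fall and also counts in the attrition rate. A reader might infer that negative effects go unrecorded in anyone who stops early, or that such couples never contribute. The documents do not support that. What remains is that the weekly data are not attributed to the PPI and are assigned to no tolerability report. In a trial that requires depressive symptoms in at least one partner, a low weekly mood score does not by itself show that an activity caused it.

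A second reply also stands. Stopping the activities is not the same as missing T2. The protocol does not make T2 attendance conditional on finishing the 8 weeks, so calling this a completers-only result goes beyond the text. The supportable description is couples who attend T2.

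Third, the weekly survey appendix and some other parts of the document were not available. An equivalent question or an adverse-event procedure may be there.

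Fourth, these items are presented as acceptability, and no negative-effects rate is a stated endpoint. That limits the consequence but does not remove it, because the plan intends to collect and use the answers.

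**Conclusion.** The point holds in a limited form. On the available text, negative effects are asked about explicitly only after treatment, and nothing is described for couples who leave. The stated results will come mainly from couples who attend T2 and may understate negative effects. Benefit and satisfaction may be overstated in the same way, but the documents do not establish that they will be.

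The gap affects at most 7 (20%) to 11 (31%) of 35 couples, on the protocol's own retention figures. A reader might take 31% as the size of the bias. It is not: it uses only the more cautious retention figure, assumes that every loss falls after the PPI starts and before T2, and becomes a rate of negative effects only if every lost couple had one. The illustrative rates of 8.0% to 16.0% against a reported 5% rest on assumed values, and the gap disappears if leaving is unrelated to negative effects.

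If the appendix already contains an equivalent weekly item, the sponsor need only cite it and state the denominator.

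**What to change.** When a couple stops the activities or withdraws, record the reason and offer each partner the same negative-effects and satisfaction questions as at T2. This can be done by phone, for example at the weekly call that already takes place. Report negative effects, and stopping because of them, over all couples who started the PPI, and state how many did not answer.

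A standing negative-effects item on every weekly call is not needed for this. It could prime answers on the same call that collects mood data.

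The cost is one brief contact per departing couple and a REDCap field. Some couples who leave will not respond, so the gap will narrow rather than close; reporting the non-responders keeps that visible. The visit schedule and the planned models are unchanged.
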